## 8.4.2 Secondary Efficacy Analyses

### Responder Rate

The number and percentage of subjects with at least a 50% reduction in migraine days will be summarized by device group, for each study phase (DB, 3 month OL, 6 month OL). The difference between the two device groups in will be compared using a two-sided, 95% CI (active minus sham). The p-value will be calculated using Fisher's exact test. If the p-value from the resulting exact test is <0.05, then the null hypothesis will be rejected.

As a sensitivity analysis, for responder rate in the DB phase, the two treatment groups will be compared using logistic regression analyses with an indicator for achieving at least a 50% reduction in migraine days (0 indicates no, 1 indicates Yes [event]) as the dependent variable and treatment group and center as fixed effects with number of migraine days in the 4-week run-in period as a covariate and again with treatment group, center, and aura as fixed effects with number of migraine days in the 4-week run-in period as a covariate.. The adjusted proportions, odds ratio, and 95% CIs f will be reported.

In addition, summary statistics and two-sided 95% CI will be produced for the following secondary effectiveness outcome measures and compared between the two treatment groups:

- The percentage reduction in migraine days during each time period (DB, 3 month OL, and 6 month OL) compared to the run-in period.
- The number of headache days during each time period (Run-in, DB, 3 month OL, and 6 month OL) as well as the change in number of headache days from the four week run-in period.
- The number of days in which acute headache medications were used during each time period (Run in, DB, 3 month OL, and 6 month OL); and, the change in the number of days from run-in.
- Scores at each visit and change in quality of life from run-in to each assessment as measured by the EQ-5D-5L, HIT-6, and MIDAS.

In addition, similar summaries may be produced for change in outcomes reported from the end of the DB period to assessments in the OL period.

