### 2.2 Secondary Objectives

The secondary objectives are:

- To evaluate the rate of responders for the gammaCore®-R group compared to the sham group. A responder is defined as recording at least 50% reduction in migraine days during the last four weeks in the twelve-week randomization period compared to the four week run-in period.
- To evaluate the difference between the gammaCore®-R and sham treatment groups in mean reduction in number of headache days during the last four weeks in the twelve-week randomized period compared to the four week run-in period.
- To evaluate the difference between the gammaCore®-R and the sham treatment groups in the mean reduction in acute headache medications taken during the last four weeks in the twelve-week randomized period compared to the four week run-in period.
- Compare improvement in headache disability using Headache Impact Test-6 (HIT-6)
- Compare improvement in Migraine Disability Assessment (MIDAS)
- Compare Quality of Life EQ-5D-5L
- Reduction of number of headache/migraine days in the open label period compared to baseline run-in period and the randomized period

- Adverse events

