## 3. STUDY DESIGN

### 3.1 Study Design

This is a prospective, randomized, sham-controlled, multi-center investigation designed for comparison of two parallel groups, gammaCore®-R (active treatment) and a sham (inactive) treatment. The study period will begin with a four week run-in period, during which there is no investigational treatment. The purpose of the run-in period will be to establish the baseline for comparisons. The run-in period will be followed by a 12 week randomized period when the subjects will be randomized (1:1) to either active treatment or sham (inactive) treatment. Figure 1 graphically displays the study design.

The randomized period will be followed by a 24 week open label period, where the subjects in the sham treatment group will switch treatment assignment and receive a gammaCore®-R device and the gammaCore®-R group will continue to receive an active treatment (See Protocol Section 7.1 for details).

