### 3.5 Sample Size

Table 1 provides the required sample size per treatment group when the number of migraine days per 28-day period is used as the primary outcome measure. Sample size calculations are based on the clinically meaningful difference between active and sham treatment groups in change from baseline. Assuming a type I error of 5% (two-sided) and 90% power, Table 1 displays the required sample sizes for different values of the common standard deviation (2.0, 2.5, 3.0 and 3.5) and the presumed difference between treatment groups (1, 1.5 and 2 days). Selecting an improvement of 1 day and a common standard deviation of 2.5 requires 133 subjects per treatment group. With 15% drop-out during the randomized treatment period, a total of 160 subjects per treatment group (or 320 subjects total) would need to be randomized.

**Table 1: Required Sample Size per Treatment Group  
Assuming Type I Error ( $\alpha$ ) = 5% (two-sided) and 90% Power**

Variability (Common SD*, $\sigma$ )	Clinically Significant Improvement: Active – Sham = $\Delta$		
	1-day	1.5-day	2-day
2.0	86	--	--
2.5	133	60	34
3.0	191	86	49
3.5	259	115	66

\*Estimated standard deviation for change from baseline. Standard deviations for baseline and post treatment scores are between 2.0 to 3.5.

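### On its natural reading, SAP section 8.4.2 applies the active-minus-sham responder test and rejection rule at open-label months 3 and 6, when both arms use the active device

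*SAP*

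**What the plan says.** Under Responder Rate, SAP section 8.4.2 asks for the count and percentage of subjects with at least a 50% reduction in migraine days, "summarized by device group, for each study phase (DB, 3 month OL, 6 month OL". The sentences that follow specify a two-sided 95% interval for active minus sham and a Fisher's exact p-value, and then the decision rule: "If the p-value from the resulting exact test is <0.05, then the null hypothesis will be rejected". None of them names a phase. The next paragraph, on the logistic sensitivity analysis, is expressly limited to the double-blind phase.

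Section 3.1 says that after the 12-week randomized period "the subjects in the sham treatment group will switch treatment assignment" and receive the active device, while the active arm continues on it.

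The open-label objective in section 2.2 is: "Reduction of number of headache/migraine days in the open label period compared to baseline run-in period and the randomized period".

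Section 7.4.2 groups open-label results by randomized arm and sets two carry-forward rules. With fewer than 70 open-label days, the open-label month 3 value is set to the double-blind month 3 value. With fewer than 154 days, the month 6 value is set to the open-label month 3 value.

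For the other secondary outcomes, section 8.4.2 asks for summary statistics and 95% intervals compared between groups, open-label periods included, and names no test. For change from the end of the double-blind period, it says only that similar summaries may be produced. The subsection on shift in MIDAS categories sets a chi-square test at each later assessment.

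**The concern.** No sham arm exists after week 12, so an open-label contrast labelled active minus sham does not estimate a device effect, and rejecting its null hypothesis does not show one. The label and the rule invite two wrong conclusions. A non-significant result at month 3 or 6 could be read as loss of effect, when it may only mean that the former-sham subjects caught up. A significant result could be read as sustained superiority over sham, when it could reflect the timing of the start, carry-over from the blinded period, or sham-period values carried forward.

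The open-label objective asks for change from run-in and from the randomized period. A between-arm responder test answers neither part.

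**Working it through.** **1. The plan's own figure.** Inputs from section 3.5: difference 1 day, SD 2.5, two-sided 5%, 90% power. The normal approximation gives 2 × (1.960 + 1.282)² × 2.5² / 1² = 131.4, so 132. The noncentral-t formula gives 133, as stated ("Selecting an improvement of 1 day and a common standard deviation of 2.5 requires 133 subjects per treatment group"). Allowing for 15% drop-out, 133 / 0.85 = 156.5, so 157; the plan randomizes 160. Expected completers are 160 × 0.85 = 136 per arm, the figure used below. The sample size itself is not in question.

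**2. What each test compares.**

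| Phase | Randomized to active | Randomized to sham | What the contrast measures |
|---|---|---|---|
| Double-blind | active | sham | device versus sham |
| Open-label month 3 | active | active | early versus delayed start |
| Open-label month 6 | active | active | early versus delayed start |

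**3. Behaviour of the test with equal open-label rates.** Exact enumeration of Fisher's test at 136 per arm, rejecting below 0.05:

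| True responder rate, both arms | Probability of rejection |
|---|---|
| 0.20 | 0.035 |
| 0.30 | 0.036 |
| 0.40 | 0.039 |

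This is the test's false-positive rate. However effective the device is against sham, the open-label test has no power to show it if both arms respond equally on the device.

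**4. Effect of carry-forward.** Assumptions, not in the SAP: the true open-label response is 0.35 in both arms; double-blind response is 0.35 active and 0.20 sham; and the same fraction f of values is carried forward in each arm. The former-sham rate becomes (1 − f) × 0.35 + f × 0.20, while the active-active rate stays at 0.35. For f = 20%, 0.80 × 0.35 + 0.20 × 0.20 = 0.32, a false difference of 0.03.

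The last two columns do the same for migraine days. They assume equal open-label means and a double-blind difference equal to the design value of 1 day, so the false difference is f × 1 day. The standard error is 2.5 × √(2/136) = 0.303.

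| f carried forward | False difference in responder rate | Fisher rejects | False difference, days | 95% interval excludes zero |
|---|---|---|---|---|
| 0% | 0 | 0.037 | 0 | 0.050 |
| 10% | 0.015 | 0.043 | 0.1 | 0.063 |
| 20% | 0.030 | 0.063 | 0.2 | 0.101 |
| 30% | 0.045 | 0.098 | 0.3 | 0.168 |
| 50% | 0.075 | 0.224 | 0.5 | 0.378 |

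The SAP names no test for the open-label change in days. The last column therefore shows how often the planned interval would mislead, not the error rate of a planned test.

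**5. MIDAS shift.** Section 7.4.2 schedules MIDAS at V6, V10 and V12, so the chi-square at each later assessment reaches the open-label visits V10 and V12. The SAP does not say whether it compares arms. If it does, the table in step 2 applies to it as well.

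**The case against.** **The text may mean the double-blind phase only.** The phase list is attached to a summary, and the p-value and null hypothesis are in the singular. The comparison sentence appears to lack words and names no phase. Section 2.2 defines the responder objective, and section 7.4.2 the response indicator, for the last four weeks of the randomized period. Section 3.4 schedules the primary and secondary efficacy analysis before the open-label period ends. This has weight, and the text is not fully explicit. But the next paragraph limits the sensitivity analysis to the double-blind phase and the main test carries no such limit, so the all-phases reading is the natural one. If the narrower meaning was intended, the SAP still needs to say so.

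**A comparison by randomized arm is legitimate.** This stands. It describes early versus delayed start, and the SAP states both the switch and the grouping. The fault is the active-minus-sham label together with an unrestricted decision rule.

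**The carry-forward effect is modest.** This also stands at 10% to 20% carried forward, where Fisher rejection is 0.043 to 0.063. The fractions and response rates are assumptions.

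Two stronger readings are tempting and are not supported. A reader might infer that every open-label outcome is formally tested; for change and count outcomes section 8.4.2 gives intervals compared between groups, with no p-value or rejection rule. A reader might also infer that the open-label objective has no analysis. Sections 7.4.2 and 8.4.2 do provide change from run-in at open-label months 3 and 6; only change from the double-blind period is left optional.

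**Conclusion.** The point holds for the responder rate. On the natural reading of section 8.4.2, two of three Fisher tests with a rejection rule carry the label active minus sham when both arms use the active device. They can speak only to early versus delayed start. With equal open-label rates they reject at 0.035 to 0.039; with 20% to 30% of values carried forward, on the assumed rates, they reject at 0.063 to 0.098 with no true open-label difference. The design argument needs none of these assumptions; only the size of the carry-forward effect depends on them.

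The MIDAS chi-square raises the same issue at V10 and V12, but only if it compares arms. The primary analysis and the double-blind responder analysis are unaffected. Nor should a reader infer an inflated error rate for the primary claim: the primary t-test in section 8.4.1 has its own decision rule, which does not depend on the open-label tests.

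**What to change.** - In section 8.4.2, limit the Fisher test, the rejection rule and the active-minus-sham label to the double-blind phase. Do the same for the MIDAS chi-square if it compares arms, and state what it compares.
- For open-label months 3 and 6, report results by original assignment, labelled active-active and delayed-active, with within-arm 95% intervals for change from run-in and from double-blind month 3.
- Make the change-from-double-blind summaries a commitment by replacing may with will, so that they meet the section 2.2 objective.
- Present any between-arm open-label contrast as descriptive, labelled early versus delayed start, without a rejection rule.

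The cost is SAP wording and table shells. Data collection, sample size and trial conduct do not change. The responder tests carrying a rejection rule fall from three to one.

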### **8.4 Efficacy Analyses**

#### **8.4.1 Primary Efficacy Analysis**

The primary efficacy analyses will be performed on the ITT population and will be repeated in the PP population, if the sample size between the two groups differ by more than 5%.

Summary statistics for the primary variable, change from 4-week run-in period, will be presented by treatment group. Missing data will be imputed per section 7.4.1.

The number of migraine days will be summarized descriptively for each study phase (run-in and DB) and by treatment group. The summary statistics for each visit, change between the double-blind and 4-week run-in period and percentage change between the double blind and 4-week run-in period (a secondary endpoint) will be summarized by mean, standard deviation, median, minimum, and maximum.

The two-sided, 95% confidence interval (CI) of the difference between the two device groups (active minus sham) in change from 4-week run-in period will be produced and the p-value will be calculated based on a two-sample t-test. If the p-value from the two-sample t-test is less than 0.05, then the null hypothesis will be rejected.

As sensitivity analyses, the two groups will be compared using analysis of covariance (ANCOVA) models with change from 4-week run-in period as the dependent variable and treatment group, and center as fixed effects with the number of migraine days in the 4-week run-in period as a covariate and again with treatment group, center, and aura as fixed effects with number of migraine days in the 4-week run-in period as a covariate. The adjusted means, adjusted mean difference and 95% confidence interval for the adjusted mean difference based on the ANCOVA models will be reported. The p-values tests that the adjusted mean difference between groups at Month 3 equals zero will be reported.

Further sensitivity analyses will investigate the robustness of the analysis to missing data (missing data refers to data points imputed in the calculations presented in section 7.4.1) by implementing multiple imputation and the pattern-mixture model (PMM) with control-based pattern imputation as summarized by Ratitch and O'Kelly (2011). This PMM sensitivity analysis addresses the possibility that the missing data is missing not at random (MNAR), meaning the missing data is not independent of the unobserved outcomes

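### The responder null is formally rejected at p<0.05 whatever the primary result, and the SAP gives the secondary outcomes no testing order, adjustment or supportive label

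*SAP*

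**What the plan says.** Section 8.4.1 sets the primary decision rule: "If the p-value from the two-sample t-test is less than 0.05, then the null hypothesis will be rejected".

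Section 8.4.2, under Responder Rate, sets a second rule of the same form for Fisher's exact test: "If the p-value from the resulting exact test is <0.05, then the null hypothesis will be rejected". It carries no condition on the primary result. The responder rate "will be summarized by device group, for each study phase (DB, 3 month OL, 6 month OL"), and the rule does not say to which of these three phases it applies.

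For the remaining outcomes the wording is weaker: "summary statistics and two-sided 95% CI will be produced for the following secondary effectiveness outcome measures and compared between the two treatment groups". The list covers:

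- percentage reduction in migraine days ("The percentage reduction in migraine days during each time period (DB, 3 month OL, and 6 month OL) compared to the run-in period");
- headache days;
- acute-medication days ("The number of days in which acute headache medications were used during each time period");
- the questionnaires ("Scores at each visit and change in quality of life from run-in to each assessment as measured by the EQ-5D-5L, HIT-6, and MIDAS").

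No threshold or null hypothesis is given for these. The subsection on MIDAS shifts adds two shift proportions evaluated by chi-square, also without a threshold.

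The only remark on alpha is in Section 3.4. It explains why analysing the randomized period before the open-label period ends needs no adjustment; it does not address several endpoints. Section 2.2 lists the secondary objectives as unranked bullets.

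**The concern.** A formal rejection rule amounts to a claim. The SAP has two such rules for efficacy, each at the full 0.05, with nothing linking them. If the t-test misses and Fisher's test gives p<0.05, the plan says that an efficacy null has been rejected, although the trial has failed on the endpoint that it was sized for. The further outcomes are compared between groups with no statement of how much weight a favourable interval carries, so a reader of the report cannot tell a planned claim from a selected one. At stake is the error rate of the efficacy claims as a set. The primary test keeps its own 5% level.

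**Working it through.** **Design figure.** Section 3.5 uses a two-sided type I error of 5%, 90% power, a difference of 1 day and SD 2.5, and states 133 per group. The noncentral-t calculation gives 132.3, rounded up to 133, which agrees. With 15% dropout, 133/0.85 = 156.5, so 157; the SAP rounds up to 160. The 5% is thus the level of the primary comparison. The SAP states no error rate for the set of efficacy claims, so there is no such figure to reproduce.

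**A. The two tests with an explicit rejection rule (primary t-test, responder Fisher test), no effect on either.**

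- Independent: 1 − 0.95² = 9.75%.
- Correlated: 1 − P(|Z₁| < 1.96 and |Z₂| < 1.96) for bivariate normal statistics with correlation ρ. This gives 9.1% at ρ = 0.5 and 7.8% at ρ = 0.8.
- The SAP gives no correlations, so ρ is assumed. It should be positive, because Section 7.4.2 derives response from the same change score as the primary.
- Fisher's test is conservative. At 133 to 160 per group and an assumed common responder rate of 20–30%, its true size is about 3.6–3.8%. With 3.7% for the responder test:

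| ρ | Both at 5% | Responder at 3.7% |
|---|---|---|
| 0 | 9.75% | 8.5% |
| 0.5 | 9.1% | 8.0% |
| 0.8 | 7.8% | 6.9% |

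Subtracting the primary's 5% from the middle column gives the chance that the responder null is falsely rejected while the primary is not significant: 9.75 − 5 = 4.75% at ρ = 0, 4.1% at 0.5 and 2.8% at 0.8.

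**B. If the interval-only outcomes were also read as tests.** Section 8.4.2 lists seven double-blind outcomes besides response: percentage reduction, headache days, acute-medication days, HIT-6, MIDAS total, EQ-5D index and EQ-5D VAS. With the responder rate that makes eight. With no effect on any of them:

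- independent: 1 − 0.95⁸ = 33.7%;
- equicorrelated normal statistics: 25% at ρ = 0.5 and 19% at ρ = 0.7.

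Adding the two MIDAS shift tests makes ten: 1 − 0.95¹⁰ = 40.1% if independent, 28.7% at ρ = 0.5.

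**C. Effect of a gate.** Suppose the responder null is tested only after a significant primary.

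- If the primary null is true, any false formal rejection requires a false primary rejection first, so the chance is at most 5%.
- If the primary effect is real and the responder null is true, the only possible false rejection is the responder test itself, again at most 5%.

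The sequence of primary then responder therefore holds the formal claims at 5% in both cases.

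**The case against.** The strongest reply is that only one secondary outcome has a rejection rule. For the other seven the SAP promises intervals and a comparison, without a null or threshold, so the 19–34% range counts rejections that the plan never makes. That stands: the size attributable to the stated rules is A, and B is conditional on how the results are read.

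A reader might also infer that a false secondary claim is likely. The documents do not support this. Even B stays below one half, needs no effect on any of the eight outcomes, and rests on assumed correlations. Nor does the SAP promise 5% control across all endpoints: the 5% in Section 3.5 belongs to the primary, and Section 3.3 states only the primary hypothesis.

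A testing order may exist in the protocol, which is not at hand. The SAP refers to none, and its unconditional responder rule would conflict with one that placed response after the primary.

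What the reply does not remove is the second rejection rule at full alpha with no gate. That is something the SAP states, so it is not a matter left to another document.

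**Conclusion.** The point holds in a limited form. As written, Section 8.4.2 permits formal rejection of the responder null after a failed primary, and the SAP does not say what standing the other secondary results have. From the two stated rules alone, the chance of a false efficacy rejection rises from 5% to about 8–10%, or about 7–8.5% with Fisher's conservatism. This assumes no effect on either endpoint and a correlation between 0.8 and 0. The 34%, 25% and 19% figures describe a possible misreading of the interval-only outcomes; they are not the error rate of the plan's own rules. The primary analysis is unaffected. The change should be made before unblinding, which Section 4 already sets as the limit for finalising the SAP.

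**What to change.** In Section 8.4.2:

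1. State that the responder null for the double-blind phase is formally tested at two-sided 0.05 only if the primary test is significant. Otherwise report Fisher's p-value as nominal.
2. State that all other secondary comparisons, including the MIDAS shift chi-square tests and every open-label comparison, are supportive, with unadjusted 95% confidence intervals and nominal p-values.

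If the sponsor wants formal claims on headache days and acute-medication days, they can be added to the sequence after response, with a named test for each. This is optional and is not needed to close the gap.

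The cost is SAP wording. Sample size and primary power do not change. The downside is that the responder result becomes descriptive if the primary fails; if the sequence is extended, each later outcome likewise becomes descriptive once an earlier one misses.

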**Figure 1: Diagram of Study Design**

### 3.2 Randomization

Subjects will be randomized to either the active treatment arm or sham control arm (allocation 1:1) under a randomized variable block design, stratified by study site.

Subjects will be randomized using Merge eClinical OS Interactive Web Response system (IWRS) via computer key board data entry for a web based interface.

The site personnel (the investigator or his designee) will enter the required study and subject information and will then be provided with a subject randomization number and device serial number. Once subject numbers, serial numbers, and randomization numbers have been assigned, they cannot be reassigned.

The IWRS will provide the site personnel confirmation of the randomization number and device serial number assigned to each subject.

A sponsor designee will also have a copy of the randomization schemes for each study site and will be responsible for providing the un-blinded trainer with the randomization schemes.

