#### *Headache Days and Headache Medications*

Change from run-in to the last 4 weeks of the randomized period in the number of headache days (as opposed to migraine days) is another secondary endpoint and will be calculated in the same manner as the primary endpoint.

The number of days in which acute headache medications were used; and, the change in the number of days from run-in to the last 4 weeks of the randomized period are also secondary endpoints. Similar to the primary endpoint, an indicator of acute headache medication usage is collected in the e-diary and the number of days of usage and the change in the number of days from run-in to the last 4 weeks of the randomized period will be calculated in the same manner as the primary endpoint. In addition, the number of days in which 1) simple analgesics (aspirin, paracetamol, ibuprofen, NSAIDs), 2) triptans and ergots, 3) combined analgesics, and 4) opioids were used, and the change in number of days from run-in to the last 4 weeks of the randomized period will be analyzed similarly.

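### Five secondary outcomes are compared between arms only as unadjusted value and unadjusted change; ANCOVA on each outcome's own baseline and center would be more precise and give one estimate

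*SAP*

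**What the plan says.** SAP 8.4.2, under Responder Rate, closes with a list of further secondary outcomes, for which "summary statistics and two-sided 95% CI will be produced for the following secondary effectiveness outcome measures and compared between the two treatment groups".

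- Headache days: the number in each period, "as well as the change in number of headache days from the four week run-in period".
- Acute medication: "The number of days in which acute headache medications were used during each time period", and the change from run-in.
- Questionnaires: "Scores at each visit and change in quality of life from run-in to each assessment as measured by the EQ-5D-5L, HIT-6, and MIDAS".

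No test, model or covariate is named for these outcomes.

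Adjusted models do appear elsewhere in the SAP. For migraine days, 8.4.1 says that "the two groups will be compared using analysis of covariance (ANCOVA) models with change from 4-week run-in period as the dependent variable", with treatment and center as fixed effects and run-in migraine days as covariate; a second model adds aura. Appendix 1 repeats ANCOVA after multiple imputation and after the control-based pattern mixture model. For the double-blind responder rate, 8.4.2 plans logistic regression with "treatment group and center as fixed effects with number of migraine days in the 4-week run-in period as a covariate", and again with aura. All of these are sensitivity analyses, and none is extended to the five outcomes.

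Section 3.2 randomizes "under a randomized variable block design, stratified by study site".

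**The concern.** In a randomized comparison, the difference in Month 3 (or V6) values and the difference in changes from baseline estimate the same treatment effect. On the same subjects, they differ by exactly the chance difference between arms at baseline. Neither uses the baseline efficiently: the value ignores it, and the change subtracts it in full whatever its correlation with the outcome. ANCOVA uses the estimated slope instead, and gives the same treatment effect whether the dependent variable is the value or the change.

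Two things follow. The intervals for the secondary outcomes are wider than they need be, and the site factor that governed randomization is left out. Where the plan does not say which of the two estimates leads, a reader has two intervals for one question and may quote the more favorable one.

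**Working it through.** **The plan's own figure.** Section 3.5 uses a difference of 1 day, SD of change 2.5, two-sided 5% and 90% power. The normal approximation gives 132 per group and the noncentral-t calculation gives 133, the stated number. Dropout of 15% gives 133/0.85 = 156.5, so 157, which the plan sets at 160. The 133 is therefore the evaluable number per arm that the plan relies on, and it is used below. The plan gives no sizing for the five outcomes.

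**Assumptions not in the SAP.** Equal SDs at baseline and follow-up, a baseline-to-outcome correlation rho of 0.3 to 0.7, and a true effect of 0.3 SD.

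**Variance of the treatment difference, in units of the value comparison.**
- Value: 1
- Change: 2(1-rho)
- ANCOVA: 1-rho²
- ANCOVA relative to change: (1-rho²)/[2(1-rho)] = (1+rho)/2

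**Power.** SE of the value difference = sqrt(2/133) = 0.1226 SD, so 0.3/0.1226 = 2.446. Power = Φ(2.446/√V - 1.96), where V is the variance factor above.

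| rho | V change | V ANCOVA | ANCOVA/change variance | Power, value | Power, change | Power, ANCOVA |
|---|---|---|---|---|---|---|
| 0.3 | 1.40 | 0.91 | 0.65 | 68.7% | 54.3% | 72.7% |
| 0.5 | 1.00 | 0.75 | 0.75 | 68.7% | 68.7% | 80.6% |
| 0.7 | 0.60 | 0.51 | 0.85 | 68.7% | 88.5% | 92.9% |

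Against the better of the two unadjusted comparisons, the gain is 72.7 - 68.7 = 4.0 points at rho 0.3, 80.6 - 68.7 = 11.9 at 0.5, and 92.9 - 88.5 = 4.4 at 0.7. Over a wider rho of 0.2 to 0.8, the ANCOVA variance is 0.60 to 0.90 of the change-score variance. Any gain from center is not counted.

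**How far value and change can differ.** Their gap is the chance baseline difference, with a 95% range of ±1.96 × 0.1226 = ±0.24 SD. The two statistics correlate at sqrt((1-rho)/2), which is 0.59, 0.50 and 0.39 at rho 0.3, 0.5 and 0.7. From the bivariate normal at a 0.3 SD effect, one 95% CI excludes zero and the other does not in 29% to 31% of trials. With no effect, at least one excludes zero in 8.8% to 9.4%.

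**Which estimate leads, outcome by outcome.**
- Headache days: section 2.2 speaks of mean reduction, and 7.4.2 names as the endpoint "Change from run-in to the last 4 weeks of the randomized period in the number of headache days". Change leads.
- HIT-6 and MIDAS: section 2.2 speaks of improvement, and 7.4.2 defines change scores. Change leads by implication.
- Acute-medication days: section 2.2 speaks of mean reduction, but 7.4.2 makes both the number of days and its change secondary endpoints. Open.
- EQ-5D-5L: section 2.2 asks only for a comparison of quality of life; 7.4.2 says that changes in score and VAS will be calculated. Open.

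**The case against.** The strongest reply is that the raw values are table rows and not rival tests. The 8.4.2 list for day counts includes the run-in period itself, where no treatment effect exists. Responder rate gets a named test and a 0.05 rule; these outcomes get only summaries and an interval. This largely stands: the 29% to 31% and the 8.8% to 9.4% describe how pairs of intervals would read, not an error rate of any test in the plan. Still, the instruction to compare between groups covers the whole list, and a 95% CI that excludes zero will be read as significant.

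Second, the objectives already favor change for most outcomes. That stands for headache days, HIT-6 and MIDAS, and narrows the ambiguity to acute-medication days and EQ-5D-5L. It does not touch the precision loss.

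Third, the unadjusted double-blind comparisons are unbiased by randomization, and the primary test is itself an unadjusted t-test, so adjustment may look like preference. Unbiasedness stands. However, the SAP already accepts this ANCOVA for migraine days, and the baselines are collected.

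Fourth, the identity between the gap and the baseline difference needs the same subjects. Someone with fewer than 21 run-in diary days, or an incomplete V2 questionnaire, has no change but may have a later value. This stands as a qualification.

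A reader might infer that the SAP has no baseline-adjusted analysis at all. It does, in 8.4.1, 8.4.2 and Appendix 1, for migraine days and responder rate. Section 7.4.2 does derive headache and medication days as for the primary endpoint, but that concerns computing the variable and does not carry the ANCOVA over.

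**Conclusion.** The concern holds for these five outcomes as a loss of precision, with a smaller problem of an undesignated lead estimate for acute-medication days and EQ-5D-5L. At rho 0.5 and 133 per arm, power for a 0.3 SD effect would rise from 68.7% to 80.6%; across rho 0.3 to 0.7, the gain over the better unadjusted comparison is about 4 to 12 points. The sizes rest on the assumed rho, effect and equal SDs. The direction does not: apart from a negligible cost in degrees of freedom, ANCOVA variance exceeds neither of the other two at any rho.

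It would be tempting to conclude that the type I error of the secondary tests rises from 5% to about 9%. The SAP does not support that, because it attaches no p-value or decision rule to these outcomes. The primary conclusion is unaffected.

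**What to change.** In SAP 8.4.2, make the double-blind (Month 3 or V6) comparison of headache days, acute-medication days (total and by class), HIT-6, MIDAS, EQ-5D-5L index and EQ-5D VAS an ANCOVA. Use treatment and center as fixed effects, with centers pooled as in 8.4.3.6, and the outcome's own run-in or V2 value as covariate. Report the adjusted mean difference with its 95% CI as the single between-group estimate. Keep raw values and raw changes as descriptive summaries by arm, without between-group inference.

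The cost is a change of wording and a model of the kind already planned for migraine days; no new data are needed. The adjusted difference will not equal the plain difference of the tabulated means, so a table footnote should say so. Subjects without a baseline value drop out of the model, as they already do for change.
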